Isokinetic Assessment of Wrist Muscles Performance among Egyptian Physical Therapy Students with Chronic Non-Specific Neck Pain

Thesis

Submitted to the Department of Biomechanics in Partial Fulfillment of the
Requirements for the Master Degree in Physical Therapy

By

[name]

Teaching Assistant, Department of Biomechanics,
Faculty of Physical Therapy, Kafr El Sheikh University
B.Sc., Physical Therapy, Cairo University, 2018

Supervisors

[name] [name]

Professor and Head of Physical Therapy Department
of Musculoskeletal Disorders and Its Surgery
Physical Therapy Department of Musculoskeletal
Disorders and Its Surgery
Faculty of Physical Therapy
Cairo University

[name] [name]

Professor and Head of Biomechanics
Department
Biomechanics Department
Faculty of Physical Therapy
Kafr El Sheikh University

[name] [name]
Lecturer of Biomechanics
Department of Biomechanics
Faculty of Physical Therapy
Cairo University

**Faculty of Physical Therapy
Cairo University
2024**

Data analysis and statistical design

Data were expressed as mean \pm SD. Unpaired t-test was used to compare between subjects characteristics of the two groups. One way MANOVA was used to compare measured variables between the two groups. Statistical package for the social sciences computer program (version 20 for Windows; SPSS Inc., Chicago, Illinois, USA) was used for data analysis. *P* less than or equal to 0.05 was considered significant.

CHAPTER IV

RESULTS

The main aim of this study was to assess the effect of chronic non-specific neck pain on peak torque of wrist extensor and flexor muscles /body weight, extensor / flexor wrist ratio and on wrist extensor and flexor muscles endurance among Egyptian physical therapy students.

Demographic data of subjects:

A total of 44 students participated in this study; they were assigned into 2 equal groups, Group A, study group, was include twenty two students with chronic non-specific neck pain (CNSNP) and Group B, control group, was include students without CNSNP.

As shown in table (1) and figures (1-4); the mean values of age of groups A and B were (20.6 ± 1.8) and (20.5 ± 1.7) years respectively, and of weight were (68.6 ± 10.7) and (72.1 ± 12.5) kg respectively, the mean values of height of groups A and B were (170.5 ± 7.8) and (171.2 ± 10.3) cm respectively, and of BMI were (23.4 ± 2.4) and (24.7 ± 3.1) kg/m^2 respectively. There were no significant differences between both groups of mean age, weight, height and BMI ($p > 0.05$).

Table (1): Subjects characteristics of both groups

Measurd variable	Group A Mean \pm SD	Group B Mean \pm SD	t-value	p-value
Age (years)	20.6 ± 1.8	20.5 ± 1.7	0.085	0.933
Weight (kg)	68.6 ± 10.7	72.1 ± 12.5	-1	0.314
Height (cm)	170.5 ± 7.8	171.2 ± 10.3	-0.247	0.806
BMI (kg/m^2)	23.4 ± 2.4	24.7 ± 3.1	-1.47	0.149

[figure not shown]

Fig 1: mean values of subjects age of both groups

[figure not shown]

Fig 2: mean values of subjects weight of both groups

[figure not shown]

Fig 3: mean values of subjects height of both groups

[figure not shown]

Fig 4: mean values of subjects BMI of both groups

Normality test:

Data were screened for normality assumption, homogeneity of variance, and presence of extreme scores. Shapiro-Wilk test for normality showed that all measured variables are normally distributed, so one way

MANOVA for between groups' comparison and Pearson coefficient correlation for finding the relation between variables were used.

Table (2): Comparison of mean values of measured variables between groups.

Work fatigue (%)				
Flexion 60°/sec	15.96 ± 16	13.8 ± 15.7	2.16	0.658
Flexion 180°/sec	14.5 ± 33	4.14 ± 26	10.36	0.260
Extension 60°/sec	8.4 ± 16	0.25 ± 15	8.15	0.095
Extension 180°/sec	4.95 ± 25	1.6 ± 36	3.35	0.725

II- Effect of CNSNP on work fatigue:

As shown in table (2) and demonstrated in figures (7 and 8), the mean values \pm SD of work fatigue of wrist flexion at (60 and 180°/sec) for subjects in groups A and B were (15.96 \pm 16 and 14.5 \pm 33) and (13.8 \pm 15.7 and 4.14 \pm 26) % respectively. The mean values \pm SD of work fatigue of wrist extension at (60 and 180°/sec) for subjects in groups A and B were (8.4 \pm 16 and 4.95 \pm 25) and (0.25 \pm 15 and 1.6 \pm 36) % respectively. There was statistical non-significant difference in the mean values of work fatigue of wrist flexion and extension at 60 and 180°/sec between both groups ($P>0.05$).

[figure not shown]

Fig 7: mean values of wrist flexors work fatigue of the two groups

[figure not shown]

Fig 8: mean values of wrist extensors work fatigue of the two groups

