Nevertheless, there is another opinion that says there is no association between forward neck posture and pain in adolescents (**Mahmoud et al., 2019**). Neck flexion while using a smartphone device (also known as "text neck") is also not associated with pain in adolescents (**Damasceno et al., 2018**).

In Egypt, a study conducted among medical students showed that 81.1% of participants experienced neck pain and/or low back pain. This pain was primarily attributed to long hours of studying and reading, especially in the clinical years. Participants also reported ergonomic problems and poor psychological studying environments (**Alian et al., 2021**). The study found gender differences in pain intensity and prevalence, with males reporting a higher prevalence of lifetime lower back pain (**AlShayhan & Saadeddin, 2018**) while females had a higher prevalence of neck and shoulder discomfort, as well as pain or numbness in their wrists (**Mustafaoglu et al., 2021**).

In **2022, Ortego et al** hypothesized that there is a notable association between neck problems and upper limb disabilities, although the mechanisms underlying this correlation are not yet well understood. Potential factors contributing to this association include deconditioning, peripheral nerve injuries, and mechanical stress.

The upper limb is mechanically connected to the neck and shoulder girdle via the skeletal and muscular systems. Mechanical loading of the upper limb may directly cause discomfort in the neck by increasing stress on the ligamentous and articular structures, or by inducing muscle spasm as a protective response (**Kumar et al., 2018**).

Non-specific neck pain is significantly associated with impaired performance of the muscles in the upper limb, leading to upper limb disability (**Alreni et al., 2015**). Upper limb disability (ULD) is a term used to describe the limitations someone experiences while engaging in physical activities related to the upper limb, such as carrying, lifting, and overhead movements. Adequate upper limb strength, endurance, and proprioception are essential for performing many job-related tasks effectively (**Gillen & Nilsen, 2020**). There was a study has shown that neck pain can lead to imbalances in muscle function, instability in joints, and reduced proprioception in the upper limb (**Tabbert et al., 2022**).

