Neck pain is a prevalent and burdensome condition that can result from a variety of factors. According to a recent study, the most common causes of neck pain include muscle strain and tension, poor posture, and degenerative changes in the cervical spine (Lawrence et al., 2022). In addition, psychological factors such as stress and anxiety can contribute to the development of neck pain and can exacerbate existing symptoms (Ortego et al., 2016). Other risk factors for neck pain include age, gender, and occupation, with individuals in physically demanding jobs or those that require prolonged periods of sitting at a desk being at higher risk (Lawrence et al., 2022; Ortego et al., 2016).

Neck pain is a widespread issue that can lead to disability and decreased productivity. Recent studies suggest that neck pain is a significant problem in the workplace and can lead to decreased work performance and absenteeism (Bealas et al., 2017). In response, healthcare providers are shifting toward a more holistic approach that considers not only the physical symptoms of neck pain but also the impact on daily activities and social participation. The American Physical Therapy Association released guidelines for the management of neck pain that emphasized the importance of patient-centered care and the use of multidisciplinary approaches to address the complex nature of neck pain (Maistrello et al., 2022).

Non-specific neck pain is a common condition that can have a significant impact on upper limb function. Studies have shown that individuals with neck pain often experience reduced grip strength, decreased range of motion, and impaired hand function (Asiri et al., 2021; Bracht et al., 2017). These functional impairments may be due to muscle weakness and imbalances, altered neural activation patterns, and changes in proprioception and kinesthetic awareness (Canu et al., 2019). As a result, healthcare providers are emphasizing the importance of incorporating upper limb assessments and

interventions into the management of neck pain, with the goal of improving overall function and reducing disability (**Alreni et al., 2015; Tsang et al., 2019**).

Self-administered questionnaires are commonly used for functional assessment of neck pain in clinical practice. These tools typically focus on evaluating the individual's subjective discomfort, perceived impairment, ability to function or manage neck pain, and/or healthcare usage.

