Wrist isokinetic dynamometry has been widely used to evaluate muscle function and identify the presence of muscular imbalances in the wrist joint, particularly in individuals with upper limb disorders and injuries (**Seven et al., 2019**). The assessment of wrist isokinetic strength has been shown to be a reliable and valid tool for evaluating the strength and endurance of wrist flexors and extensors in both clinical and research settings (**Ağırman et al., 2017**).

Although it is widely acknowledged that chronic non-specific neck pain is linked to hand disability, the assessment of flexor/extensor wrist strength ratio in this group has only recently gained attention. Furthermore, there is limited research investigating the strength control ratio that incorporates both concentric and eccentric muscle actions, and additional scientific evidence is needed to establish the relationship between chronic non-specific neck pain and upper limb disability, therefore in our study, we will be conducted to examine wrist muscle performance through peak torque of wrist extensor and flexor muscles to body weight, extensor / flexor wrist strength ratio and wrist extensor and flexor muscles endurance in chronic non-specific neck pain among Egyptian college students to evaluate functional ability of wrist in the upper limb in non-specific neck pain students to set new assessment and rehabilitation goals. This will subsequently be translated into home therapy program, contributing to decrease the burden of neck pain economically and on health care management.

Chapter III

[figure not shown]
Subjects and methods

Our study aims to evaluate peak torque of wrist extensor and flexor muscle / body weight and extensor / flexor wrist ratio and wrist extensor and flexor muscle endurance among Egyptian physical therapy students with chronic non-specific neck pain. The practical part of the study is expected to be from May/2023 to December/2023 and will be conducted in the isokinetic lab in EL DELTA University.

Design: cross-section study

Sample size calculation:

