Using G-power software (version 3.1.9.7; Franz Faul, Universitat Kiel, Germany) for windows and regarding MANOVA study, alpha level of 0.05, confidence level 0.80, and effect size 0.56, calculated from the previous study of (**Agirman et al., 2017**) that used the isokinetic dynamometer for measuring the peak torque of wrist with a sample of 35, and a two-sided alternative hypothesis, the sample size is 39 patients to be able to reject the null hypothesis. If 15% dropout rate is anticipated, approximately 44 patients (twenty-two in each group) will be recruited.

1. Students' selection:

The current study will be conducted on twenty-two non-specific neck pain Egyptian physical therapy students a with referral from orthopedic surgeons by diagnosis with non-specific neck pain other twenty-two without neck pain subjects from outpatient clinic of Faculty of Physical Therapy, EL DELTA University. Students' age ranges from 18 to 23 years. Students will be selected from faculties of physical therapy. Students will be assigned into two equal groups, the study group (GA) (chronic non-specific neck pain students) and the control group (GB) (normal students). They will be instructed not to participate in any training program until the posttest.

Inclusion criteria:

- 1- Students from both genders (**Fayez, 2014**).
- 2- Duration of the non-specific neck pain is more than 3 months (for symptomatic group with no neurological manifestations and with referral from orthopedic surgeons by diagnosis with non-specific neck pain) and for matched students, they do not have any history of neck pain (**Chung & Jeong, 2018**)
- 3- Student' age ranges from 18 to 23 years.
- 4- Neck pain intensity on the numerical Pain Rating Scale will be between 3 to 8.
- 5- Neck pain-related disability on the Neck Disability Index will be between 5-14points (10 – 28%) mild disability and 15-24points (30-48%) moderate disability.
- 6- Body mass index for students will not be less than 18.5 and not more than 29.5 (**Alasadi, 2018**).

Exclusion Criteria:

Any participant suffered from one of these symptoms will be excluded:

- 1- Indications of neurological conditions (i.e., Parkinson's disease, multiple sclerosis, head injury, peripheral neuropathy, stroke, or nerve root entrapment) (**Mahmoud et al., 2020**).
- 2- Headache caused by a certain diagnosis of headache.
- 3- History of cancer, infection, or any other illness symptoms.

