- The participant's personal data will be collected. The data include the participant's name, age, address, weight, height, and phone number.
- All subjects of both groups will be tested for the isokinetic parameters twice (on dominant and non-dominant sides).
- The participant will be allowed to sit on the adjustable seat of the isokinetic dynamometer system.
- The tested arm will be placed on the limb support pad and secured with strap. Then the tested hand will be securely fastened with wrist attachments.
- The dominant hand is the one preferred by the participant to write or manipulates objects.
- Shoulder and waist straps will be placed around the chest to secure and stabilize the patient. In addition, the untested limb will be placed in a rest position and secured by strap,

Measurement of muscle performance of wrist by isokinetic dynamometer

This involves:

- 1) Measuring peak torque of wrist extensor and flexor muscles /body weight among Egyptian physical therapy students.

- 2) Measuring extensor / flexor wrist muscles ratio among Egyptian physical therapy students.
- 3) Measuring wrist extensor and flexor muscles endurance among Egyptian physical therapy students.

1- pre-experimental testing instructions:

- Before the actual isokinetic testing procedures, each participant will perform one practice series of three sub-maximal wrist extension and flexion repetitions to get accommodated with the specificity of the isokinetic speed of movement and wrist ROM. That will be done to minimize any practice effect during the actual testing procedure.

2- The isokinetic system preparation:

- The isokinetic system was powered, initialized, and calibrated.
- The dynamometer was rotated to 0° and was tilted to 0°.
- Wrist Attachment of dynamometer will be attached by placing input tube on dynamometer then it will be rotated horizontally to the floor to be aligned with the dynamometer shaft red dot.
- The testing chair was rotated to 0° degrees and seat back tilt was set to 85 degrees.
- The participant sat on the chair and the wrist axis of rotation will be aligned with dynamometer lever arm as discussed later in participant preparation.
- Axis of rotation for this pattern lies between the proximal row of the carpal, at the capitate bone, and the radius at the radiocarpal joint.

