- The isokinetic parameters will be tested at angular velocity of 60°/sec. The testing velocity was selected from the control panel. The rationale for choosing this speed was based on previous studies. The literature suggested that wrist measurements will be taken from each participant at

the points where the dynamometer equipment was adjusted at 60°/sec for measuring muscle strength and 180°/sec for measuring muscle endurance angular velocities (**Janicijevic et al., 2020**). Fast speed is for power, whereas slow speed is for strength. Reports by researchers have been employing both 60° and 120°/sec in isokinetic assessment for strength and power.

- Before being raised to this position, the dynamometer's range of motion will be adjusted to a total of 80 degrees, comprising 40 degrees of wrist flexion and 40 degrees of wrist extension (**Seven et al., 2019**).
- The concentric/concentric mode was used to measure the wrist muscles peak torques, power and endurance.

B. Experimental phase

This phase involved experimental testing procedures for measuring peak torque of wrist extensor and flexor muscles /body weight, extensor / flexor wrist ratio and wrist extensor and flexor muscles endurance among Egyptian physical therapy students.

The experimental testing procedures will be conducted for all the participants of both groups.

- Following warm up, each participant will be positioned according to the instruction described before.
- The personal data of each participant will be introduced into computer, which includes participant name, age, sex, identification number and weight.
- The test protocol that will include the wrist ROM, the testing velocities, the mode of contraction and the test repetitions will be selected from the control panel.
- Each participant will be instructed to perform five sets of wrist extension and flexion at the selected wrist ROM (60°).

- Verbal encouragement will be given during the testing procedure to maximize the participant's voluntary effort.
- Wrist extensors and flexors will be tested at the concentric mode of muscle contraction using 60°/sec angular velocity.
- A 1- min rest will be given between warm up and actual test sequence.
- Testing procedures will be performed twice, on the dominant and non-dominant sides for both the study and control groups.

C. Analysis of the captured data

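### Peak torque per body weight is compared between non-randomised groups open to both sexes, with group as the only model term; sex is neither reported by group nor adjusted for

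*SAP*

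**What the plan says.** **Model.** The SAP (Data analysis and statistical design) says "One way MANOVA was used to compare measured variables between the two groups". It mentions no second factor, covariate or stratum. Subject characteristics are compared by unpaired t-test only.

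**Design.** Chapter III of the protocol gives "Design: cross-section study". Groups A and B are students with and without chronic non-specific neck pain, so nothing was randomised. The first inclusion criterion is "Students from both genders", with no quota or stratification.

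**Matching.** The second inclusion criterion contains the phrase "for matched students, they do not have any history of neck pain". No matching variable or procedure is given.

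**Sex and neck pain.** The literature review states "Other risk factors for neck pain include age, gender, and occupation". The introductory chapter adds that "females had a higher prevalence of neck and shoulder discomfort, as well as pain or numbness in their wrists".

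**Recording of sex.** Participant preparation lists personal data without it: "The data include the participant's name, age, address, weight, height, and phone number". The Experimental phase has it entered into the dynamometer computer, with a data list "which includes participant name, age, sex, identification number and weight".

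**Reporting.** SAP Table 1 and its text cover age, weight, height and BMI. The protocol's Statistical Analysis plans a chi-square test for categorical data without naming sex; the SAP contains no such test.

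**The concern.** The stated aim is to assess the effect of neck pain on wrist torque per kg. In a non-randomised comparison, a variable related to both group membership and outcome has to be balanced by design or handled in the analysis. The protocol supplies the first link, sex to neck pain. The second, sex to wrist torque per kg, is plausible but not documented.

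If it exists, two things follow. Any difference in sex mix between the groups is read as an effect of neck pain. If the mix happens to be equal, the variance due to sex stays in the error term and power is lost. A reader cannot tell which case applies, because sex by group is not in the supplied text.

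The point concerns peak torque/body weight. The strength ratio and work fatigue each compare a participant's own muscle performances with one another, so a general difference in strength between the sexes should affect them less; that is a judgement, not something the documents show.

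**Working it through.** **1. The documents' own figures.** The plan contains no calculation on sex. The nearest evidence is height in SAP Table 1: 170.5 ± 7.8 cm and 171.2 ± 10.3 cm, 22 per group.
- SE = √((7.8² + 10.3²)/22) = 2.75 cm.
- t = −0.7/2.75 = −0.25, p = 0.80. The table gives −0.247 and 0.806, which agree within rounding.
- 95% CI = −0.7 ± 2.018 × 2.75 = −6.3 to 4.9 cm.

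**2. What height implies about sex balance.** Assume a male–female height gap of 10 to 15 cm, a within-sex SD of 6 to 7 cm, and both groups drawn from one 50:50 pool.
- Compatible range for men in A minus men in B = (−0.7 ± 2.018 × SD × √(2/22)) × 22/gap. Gap 10, SD 7: −10.9 to 7.8. Gap 15, SD 6: −6.4 to 4.3.
- Given the observed heights, a difference of 4 men or fewer has probability 90% to 96%, and of 6 or more 1% to 4.5%.
- A 14 against 8 split would itself be non-significant (chi-square p = 0.07, Fisher p = 0.13), so a baseline test would not establish balance.

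**3. Bias at a given imbalance.** Let δ be the sex effect in within-sex SD, assumed 0.3 to 1.6. The low start allows for division by body weight removing part of it. Spurious group difference = (difference in men/22) × δ. For 8 against 14 men: 6/22 × 0.3 = 0.08 SD, up to 6/22 × 1.6 = 0.44 SD.

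**4. Type I error, single outcome.** Simulated with 22 per group, two-sided 5% test, no neck-pain effect, group as the only term:

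| Men, one group v the other | δ=0.3 | 0.5 | 0.8 | 1.2 | 1.6 |
|---|---|---|---|---|---|
| 11 v 11 | 4.9% | 4.4% | 3.4% | 2.2% | 1.2% |
| 10 v 12 | 4.8% | 4.5% | 4.0% | 3.0% | 2.2% |
| 9 v 13 | 5.1% | 5.3% | 5.6% | 5.8% | 5.8% |
| 8 v 14 | 5.7% | 6.5% | 8.2% | 11.4% | 14.3% |

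With sex in the model the rate is about 5% in every cell.

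Hand check of the last cell:
- Within-group sum of squares of the sex indicator = 2 × (8 × 14/22) = 10.18.
- Expected pooled variance = 1 + 1.6² × 10.18/42 = 1.62, SD 1.27.
- Critical difference = 2.018 × 1.27 × √(2/22) = 0.77. The true mean difference is 0.44 with SE 0.30.
- The upper tail beyond (0.77 − 0.44)/0.30 ≈ 1.12 is about 13%, close to the simulated 14.3%.

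**5. Type I error, sex drawn at random.** If both groups come from one 50:50 pool, the average unadjusted rate is 5.0%. With 40% men in one source population and 60% in the other, it is 5.4% to 13.2%.

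**6. The MANOVA itself.** Assume four torque/kg outcomes correlated 0.3 to 0.6. Unadjusted, 8 v 14 gives 5% to 9% and 11 v 11 gives 3% to 5%. Adjusted, the rate is about 5%.

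**7. Power with balanced sex.** For a true effect of 0.8 SD on one outcome, unadjusted power is 73%, 71%, 67%, 61% and 52% across the five values of δ. Adjusted power is about 74%.

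**8. Cost of adjusting.** One residual degree of freedom (42 to 41) for an additive sex term. At 8 v 14 the variance of the group contrast rises by 1/(1 − (6/22)²) = 1.08, and adjusted power for 0.8 SD falls from 74% to 70%.

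**The case against.** **The sex–outcome link is assumed.** This stands. The documents give no sex difference in wrist torque per kg, and at 0.3 to 0.5 SD both the inflation and the power gain are small.

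**The likely splits do little harm.** This largely stands too. If both groups come from one 50:50 pool, small imbalances are the probable ones, and they leave the test at or below about 6%. But the protocol's own statements on gender and neck pain give reason to doubt a common pool, and height does not exclude a difference of 6 men.

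**Matching and the chi-square test already cover it.** They do not. Neither names sex, and neither adjusts the torque comparison.

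**Enrolled composition and recording of sex are known only as planned.** Correct. Eligibility of both sexes and entry of sex into the computer are forward-looking statements, and the other list of personal data omits sex. This affects how easily the data can be retrieved, not whether the model lacks a sex term.

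**The supplied text is incomplete.** The torque rows of Table 2 are absent, so no torque conclusion can be shown to be at risk. The criticism is of the model. A lost sex row in Table 1 is unlikely, since its text and Figures 1 to 4 match the four characteristics listed.

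**Conclusion.** The concern holds. For a non-randomised comparison open to both sexes, the plan neither reports nor adjusts for a variable that its own background chapters link to neck pain. Confidence is high about that omission and does not extend to any actual bias, whose direction and size are unknown.

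On the assumed range of sex effects, the consequence runs from negligible, or mildly conservative with balanced sex, to roughly a doubling or near-tripling of the single-outcome error rate when the effect is large and the groups differ by 6 men. The multivariate test is less affected. Inflation on average requires a systematic difference in sex mix between the groups. This should be fixed because the comparison is a main aim of the study and the remedy is cheap.

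**What to change.** 1. Add sex by group (counts and percentages) to SAP Table 1.
2. State whether controls were matched and, if so, on which variables and how.
3. Add sex as an additive term to the model for peak torque/body weight (MANCOVA, two-way MANOVA without interaction, or ANCOVA per outcome). Report it beside the unadjusted MANOVA and label it post hoc, because results are already reported.

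**Cost.** One table row, one sentence and one SPSS re-run. Sex may first have to be transferred from the dynamometer computer to the analysis file for 44 students. The statistical price is the one in step 8 of the working; fitting a sex-by-group interaction would take a second residual degree of freedom (42 to 40). If the new table row shows sex to be balanced, the bias question is largely settled and the adjusted model mainly recovers precision.
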